Aim 1: Test intervention components through an open label pilot (N=5) of the intervention, followed by in-depth interviews. We will assess the salient features of the novel intervention components using mixed methods including examination of all quantitative measures and qualitative interviews to explore acceptability, participant/interventionist interactions, home environment factors, goal achievement and perceived value of intervention. Intervention components will be adapted for the trial participants (who will be randomized) based on results of Aim 1.

Aim 2: Conduct a single-masked, waitlist control pilot trial of the HEROIC intervention (N=44). We hypothesize that caregivers who receive the intervention will have improvement in primary outcomes (goal attainment of health behaviors, caregiver burden and QOL) and potential mechanisms (self-efficacy and heart rate variability, a biomarker of resilience) between baseline to 12 weeks (immediate intervention group) and 12-24 weeks (waitlist).

Aim 3: Assess the salient features of the intervention components and delivery using mixed methods to explore acceptability, participant/interventionist interactions, home environment factors, goal achievement and perceived value of the intervention.

3. Background

There are five significant gaps in the science of HF caregiving. First, most caregiving interventions focus on conditions like dementia, which have a predictable trajectory; HF is characterized by unpredictable exacerbations. Second, HF caregiver studies have included predominantly white, middle income caregivers. Third, current HF caregiver interventions often place additional responsibility on the caregiver and have a deficit-focus instead of a strengths-based approach. Pourth, there is a dearth of interventions that decrease emotional distress and improve preventive health behaviors of HF caregivers. Fifth, trialed interventions have had limited impact. In addition, the National Academies have called for research to meet the needs and values of diverse family caregivers and to improve caregiver health. Therefore, the purpose of this study is to improve preventive health behaviors, caregiver burden and QOL in caregivers of patients with HF through a resilience-building intervention delivered in the home (HEROIC).

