| Week 10 | Discuss how caregiver will involve social support in next goals |
| | Walking meeting (if virtual: suggest participant take a walk during call) |
| Phone Check-in | Review/edit purpose statement |
| Week 12 | Assess goal attainment and strategies to achieve goal |
| | Walking meeting (suggest participant take a walk during call) |
| Data Collection Visit | Heartrate Variability Measurement |
| Week 12 | Survey |
| Data Collection Visit | Heartrate Variability Measurement |

Week 24 Survey

Death of the Patient: If the patient/care recipient of the enrolled caregiver/study participant dies during the study, we will send a sympathy card. In that communication, we will ask the caregiver if they would like to participate a modified version of the intervention for bereavement: 1-3 visits (scheduled every other week) with a nurse for bereavement support within two months of the death of the care recipient. Additional instrumental support resources will be suggested such as grief support groups, referral to Roberta's House and bereavement resources for tasks to complete after someone you love dies. If the caregiver chooses to discontinue their participation, we will discontinue study contact and data collection. Data from caregivers whose care recipient dies will be excluded from analysis of primary and secondary outcomes.

Research Variables and Measurement

We chose measures (Table 2) based on previous RCT experience of mentors as well as those that met the following criteria: 1) possess known reliability and validity with ethnically diverse samples; 2) are sensitive to change from an intervention; 3) have clinical relevance; 4) Common Data Elements to connect this work with the broader literature and 5) represent objective as well as subjective indicators of the domains we seek to impact. Finally, we sought to achieve a balance between psychometric quality and practical considerations such as respondent burden. All instruments with the exception of demographics will be measured at baseline, 12 and 24 weeks. Patient characteristics will be obtained from chart review.

^{*} Waitlist control group will begin intervention at week 12.

Table 4: Constructs, Instruments and Reliability

| Theoretical Construct | Instruments and variables | Cronbach's alpha | | | |
|--|--|---------------------|--|--|--|
| | Contextual Factors | | | | |
| | 1)How well does the amount of money you have take care | | | | |

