- 6) Live within a 1.5 hour driving radius of the Johns Hopkins Hospital

Exclusion Criteria:

- 1) Caregivers with cognitive impairment using the six-item screener will be excluded. Severe Cognitive Impairment would make active participation in interviews and survey completion very difficult.
- 2) Non-English speakers will be excluded. Non-English speakers may have unknown needs that cannot be addressed with this intervention.
- 3) Caregivers with terminal diagnosis will be excluded as goal setting at end of life may be different than without a terminal diagnosis.

4) Caregivers who consented to IRB00203584 and participated in at least one intervention visit. These participants have received components of the intervention.

6. Drugs/ Substances/ Devices

N/A

7. Study Statistics

Exploratory and descriptive analysis will be completed for all study variables. Variables will be examined for normality and examined with means and standard deviations or medians and interquartile ranges accordingly. Baseline characteristics comparing the two groups (waitlist vs. immediate intervention) will be assessed. Any differences between the groups will be adjusted for further analysis. The significance level will be set at 0.05. Sensitivity analyses will be conducted adjusting for variables on which the group differ and compared to the pattern of results in the main analyses.

Analysis Plan:

Qualitative Analysis (Aims 1 and 3) - A qualitative descriptive analysis approach will be applied to data analysis of semi-structured interviews. 82,83 The codebook will be adjusted as needed. Similar codes will then be grouped into categories/themes that express the latent idea of grouped codes which will be used to refine the intervention protocol.

Aim 1 – In addition to qualitative analysis, descriptive analysis will be used to examine all quantitative data. Joint displays will be used to provide a structure to discuss the integrated quantitative and qualitative analysis and assist the study team in making changes to intervention components and overall protocol to improve feasibility and acceptability.⁸⁴

Aim 2 -

a. Primary outcome variable.

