Generalized estimating equations (GEE) will be used to examine the difference between intervention and waitlist groups in change from baseline to 12 and to 24 weeks for QOL (primary outcome). Time, group and the group by time interaction will be included in the model. We will also calculate Hedges' g for differences in change over time between the groups in change in primary outcomes. Hedges' g is recommended over Cohen's d' to correct of an upward bias in small sample sizes.⁸⁵ The effect size associated with the variables will be compared to established clinically significant improvement reported in the literature, rather than placing emphasis on statistical significance.

b. Secondary outcome variables.

Generalized estimating equations (GEE) will be used to examine the difference between intervention and waitlist groups in change from baseline to 12 and to 24 weeks for self-efficacy and HRV (secondary outcomes) using a similar approach (as described for primary outcome).

In addition, the correlation between the change in the mechanisms and change in primary outcomes will be examined. We will also examine cost of the intervention.

Mixed Methods Analysis - Qualitative analysis and joint displays will be used to compare those with improvement in quantitative outcomes after the intervention to those who did not have improvement to elucidate unmeasured or unpowered change as reported by participants. This mixed methods analytic approach to intervention evaluation maximizes what we will learn from the pilot by increasing understanding of context, responsiveness to ethnically and culturally diverse populations and how implementation influences outcomes. Thus, the development and testing of the HEROIC intervention will address preventive health behaviors of HF caregivers, using rigorous methods to

promote inclusivity and tailor the intervention to caregiver needs to decrease caregiver burden and improve quality of life.

c. Statistical plan including sample size justification and interim data analysis.

Sample Size:

Aim 1) For our open-label pilot we will include 5 caregivers to test intervention components, feasibility, acceptability, delivery and communication.

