Aim 2) As a pilot study, the analyses will not have adequate power to detect significant differences. Therefore, initial effect sizes, rather than statistical significance, will be examined for evidence of the effectiveness of the intervention. With a target sample size of 44, 22 in the waitlist control and 22 in the intervention, we will be able to gauge an initial estimate of the effect size associated with the intervention as compared to usual care for caregivers. Waitlist control groups are used to first provide an untreated comparison and second to allow wait-listed participants an opportunity to receive the intervention at a later date. ⁸⁷ This is especially appropriate given that very few services are currently offered to HF caregivers. We will also conduct debriefing interviews with all participants following the trial. To account for an estimated 20% attrition, we will recruit a total of 49 to the trial with the goal of 44 participants completing the study.

Understanding the factors that predict which intervention components are successfully implemented and for which participant subgroups will be critical for fine-tuning this multicomponent intervention for future proposals that will extend efficacy examinations and effect modification analyses. Acceptability of the intervention will be examined in multiple ways. We will examine percentages of people who stayed in each arm of the study and conduct numerous descriptive correlational analyses of the association between the intervention compliance and other variables. These analyses will quantify intervention implementation by demographic and participant health variables. Analyses that utilize the post-randomization data (e.g., treatment compliance) ⁴⁰⁻⁴³ will be evaluated in supplementary analyses. We will distinguish non-compliance with intervention from attrition or loss to follow-up, i.e., missing data. We will also use the participant satisfaction data to examine acceptability of the intervention.

d. Early stopping rules.

As this is a low-risk behavioral intervention pilot, we have not defined any early stopping rules.

8. Risks

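### The mechanism–outcome correlation states neither its interval nor how randomised arm is handled; computed across both arms over weeks 0–12 it would be biased towards the hypothesis, and adjusting for arm removes that bias

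*Combined protocol and SAP*

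**What the plan says.** Section 2 (Aim 2) hypothesises improvement in the primary outcomes and in "potential mechanisms (self-efficacy and heart rate variability, a biomarker of resilience) between baseline to 12 weeks (immediate intervention group) and 12-24 weeks (waitlist"). Each arm is thus considered over its own treated phase.

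Section 7 (Aim 2, b) links mechanisms to outcomes in one sentence: "the correlation between the change in the mechanisms and change in primary outcomes will be examined". It names no coefficient, interval or arm term.

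The neighbouring text does not fill the gap:

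- Under a. Primary outcome variable, the GEE model concerns "change from baseline to 12 and to 24 weeks for QOL (primary outcome"), and "Time, group and the group by time interaction will be included in the model". That group term belongs to the GEE models, which b. extends to self-efficacy and HRV. It is not carried over to the correlation.
- The opening of Section 7 says "Any differences between the groups will be adjusted for further analysis". In context this concerns baseline characteristics, not assigned arm.
- No mediation or lagged model is described.

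The data needed are already planned. Section 4 (Research Variables and Measurement) states "All instruments with the exception of demographics will be measured at baseline, 12 and 24 weeks". The analysis size is given in Section 7 (Aim 2, c): "With a target sample size of 44, 22 in the waitlist control and 22 in the intervention".

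**The concern.** The correlation is the only planned quantitative analysis that ties change in a mechanism to change in an outcome. In weeks 0–12 the immediate arm is treated and the waitlist arm is not, and Aim 2 expects treatment to improve both kinds of variable. If it does, treated participants sit higher on both changes and untreated participants lower. One correlation across everyone then picks up the gap between the arms. That gap says nothing about whether the people whose self-efficacy or HRV rose most are those whose outcome improved most.

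The bias favours the conceptual framework and grows with the treatment effect. The pilot leans on effect sizes rather than significance tests, so a biased estimate matters even if nobody tests it.

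**Working it through.** **Plan's own figure.** The plan states no correlation, effect size or power for this analysis, so there is nothing to reproduce. The documents supply the allocation (22 and 22, N = 44), the 0.05 significance level (two-sided assumed here) and the measurement times. The arm effects below are assumptions.

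**Step 1: correlation induced by combining the arms.** Let d1 and d2 be the arm differences in mechanism change and outcome change, in within-arm SD units. Set the within-arm correlation to zero. With equal arms, the difference between arms adds d1·d2/4 to the covariance and d²/4 to each variance, so

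r = (d1·d2/4) / √[(1 + d1²/4)(1 + d2²/4)].

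- d = 0.5 on both: 0.0625/1.0625 = 0.06
- d = 0.8 on both: 0.16/1.16 = 0.14
- d = 1.0 on both: 0.25/1.25 = 0.20

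For burden, where improvement lowers the score, d2 is negative and so is r.

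**Step 2: comparison with sampling error.** The critical value is t/√(df + t²). At N = 44 (df = 42) it is 0.297. Simulation used 22 per arm, 40,000 replicates and zero within-arm correlation:

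| Assumed d1 / d2 | Induced r (formula) | Nominally significant at 5%, arm ignored |
|---|---|---|
| 0.2 / 0.2 | 0.01 | 5.1% |
| 0.5 / 0.5 | 0.06 | 6.7% |
| 0.5 / 0.8 | 0.09 | 8.7% |
| 0.8 / 0.8 | 0.14 | 14% |
| 1.0 / 1.0 | 0.20 | 26% |
| 1.3 / 1.3 | 0.30 | 53% |

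By Fisher's z with standard error 1/√41, the 95% interval is about −0.24 to 0.35 around 0.06 and −0.10 to 0.47 around 0.20. With equal effects, the artefact alone reaches 0.297 when d = √[4(0.297)/(1 − 0.297)] = 1.30.

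**Step 3: arm removed.** With arm partialled out, the mean correlation in the same simulations is 0.00 and the rejection rate is 4.8% to 5.2% at every effect size tried. The critical value at N = 44 rises from 0.297 to 0.301 (df = 41).

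**Step 4: dependence on the interval.** If change is taken over each arm's own treated phase, or over weeks 0–24, both arms have been treated. If they respond alike, d1 and d2 are near zero, and so is the induced correlation.

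**Note on N.** The plan also says "To account for an estimated 20% attrition, we will recruit a total of 49 to the trial with the goal of 44 participants completing the" … Losing 20% of 49 would leave 49 × 0.8 = 39.2, about 39, where the critical value is 0.316 (0.320 with arm removed). That mismatch is a separate matter and does not alter the argument here.

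**The case against.** The strongest reply is that the plan does not prescribe the biased calculation. The sentence is silent on arm and interval, and Aim 2's own framing by treated phase points to a version in which the artefact nearly disappears. This stands. The fault is an open specification whose literal reading is biased, not a stated wrong method.

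Three further points also stand. At modest effects the artefact is lost in sampling error. The plan calls these variables potential mechanisms, says the correlation will be examined, and claims no mediation. The GEE models already give a randomised comparison of whether the intervention moves self-efficacy and HRV, so the correlation is a supplement.

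None of this removes the point. Aim 2 uses treated-phase intervals while Section 7 uses baseline to 12 and to 24 weeks, so the choice could be made after the data are seen.

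Three stronger readings are tempting, and the documents do not support them:

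- **That the trial would report a false mechanism.** This needs large effects on both variables, around 1 SD or more. The documents neither state nor exclude effects of that size.
- **That goal attainment makes the artefact large because goals are set within the intervention.** An arm effect of 2 SD on goal attainment with 0.8 SD on the mechanism would give 0.4/√(2 × 1.16) = 0.26. The 2 SD is only an assumption, and Section 7 names QOL as the primary outcome for analysis.
- **That a lagged correlation (mechanism change over weeks 0–12 with outcome change over weeks 12–24, immediate arm) would settle time order.** In that arm, weeks 12–24 measure maintenance. Only about 22 people contribute, so the critical value is about 0.42. The two changes also share the week-12 visit with opposite signs, which adds a bias of its own.

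**Conclusion.** The point holds in a limited form. The plan leaves the interval and the handling of arm unstated. The literal calculation, all participants over weeks 0–12, is biased in the hypothesised direction whenever the intervention moves both variables. The size is about 0.06, 0.14 and 0.20 in absolute value for assumed effects of 0.5, 0.8 and 1.0 SD on both, given equal arms and no within-arm association.

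The bias is minor beside sampling error at N = 44 unless effects are large, and close to zero if both arms are treated in the chosen interval and respond alike. No primary estimate, sample size or aspect of conduct changes. Because a better method is available from data already collected, this is a free improvement of low severity. Adjusting for arm removes this one artefact; shared causes and time order remain open.

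**What to change.** Replace the sentence in Section 7 (Aim 2, b) with wording such as: *The association between change in each mechanism and change in each primary outcome from baseline to 12 weeks will be estimated as a partial correlation adjusted for randomised arm (the pooled within-arm correlation), with a 95% confidence interval. This analysis is exploratory and will not be interpreted as evidence of mediation or of time order.*

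Do not add the lagged correlation. The phrase *each primary outcome* should follow whichever list the plan settles on, since Aim 2 names three outcomes and Section 7 names QOL.

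The cost is wording and one degree of freedom. No extra data are needed.

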This study is grounded in a strong theoretical basis using principles of Bandura's Theory of Self-Efficacy and the Society to Cells Resilience Model. ^{28,29} Our theoretically-driven proposal posits that contextual, caregiver and patient factors influence caregiver self-efficacy, and resilience, ^{28,29} Resilience, or positive adaptation when facing stressors, can be increased through person-centered interventions through incremental action plans to achieve goals, which can also increase self-efficacy. ^{5,30,31} Such interventions improve biomarkers of stress resilience such as heart rate variability which is related to CVD risk and self-reported outcomes such as caregiver burden and QOL. ^{32–34} In addition, articulating 'purpose in life' promotes resilience, placing the stressor in the context of larger values. ^{14,35–37} Based on these tenets, the conceptual framework ties together the many proposed levels of measurement such as context, self-efficacy, resilience, health behaviors, caregiver burden and QOL by intervening simultaneously on them to improve overall resilience (figure 1). **This flips the paradigm of caregiver intervention from a burden and difficulty focus to a strength-building and resilience focus.**

4. Study Procedures

Overview of Study Design (Figure 2): We propose an open label pilot (n=5) with a subsequent single-blind, two group randomized pilot trial to test the feasibility and gauge an initial effect size of the HEROIC intervention to improve QOL. The immediate intervention group (n=22) will receive the intervention during weeks 0-12. The waitlist control group (n=22) will be provided written materials with community resources for caregivers during the first 12 weeks, then they will begin the intervention. Waitlist control groups are used to first provide an untreated comparison and second to allow wait-listed participants an

Figure 2. Group assignment and outcome measurement

opportunity to receive the intervention at a later date.^{38,39} This is especially appropriate given that very few services are currently offered to HF caregivers. To account for estimated 20% attrition we will recruit 49 participants.

Using the NIH Stage Model for Behavioral Intervention development, this proposal is congruent with a Stage 1A and 1B level of development.⁴⁰ Development of the intervention will be made more person-centered and

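### Hedges' g is to be read for evidence of effectiveness with no measure of precision attached, although at 22 per arm its 95% interval extends about 0.59 either side

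*Combined protocol and SAP*

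**What the plan says.** The size of the randomised phase is given in section 7, item c (Sample Size, Aim 2): "With a target sample size of 44, 22 in the waitlist control and 22 in the intervention". No effect size, SD, power or precision target supports it. The same paragraph states: "As a pilot study, the analyses will not have adequate power to detect significant differences". The next sentence draws the consequence that "initial effect sizes, rather than statistical significance, will be examined for evidence of the effectiveness of the intervention".

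Section 7, Aim 2, item a (Primary outcome variable) names the measure: "We will also calculate Hedges' g for differences in change over time between the groups in change in primary outcomes". It chooses Hedges' g over Cohen's d to reduce small-sample bias. It then says that the effect size "will be compared to established clinically significant improvement reported in the literature, rather than placing emphasis on statistical significance". The benchmark has no value and no source, and the SD used to standardise g is not stated.

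Conventional inference is also present. The opening of section 7 says "The significance level will be set at 0.05", and items a and b specify GEE models with time, group and their interaction. No section links a standard error, confidence interval or p-value from those models to g.

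**The concern.** The reasoning runs from low power to reliance on the effect size. Low power at a given sample size is another way of saying that the estimate has a large standard error. Setting the significance test aside leaves that error in place and removes it from view. A point estimate compared with a clinical benchmark, with no interval, cannot separate a worthwhile effect from chance, yet the text treats it as bearing on whether the intervention works.

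What is at stake is how the pilot's results are read. A moderate g could be presented as support for the intervention when the data fit no effect, or some harm, equally well. The exposure grows with the number of outcomes: section 2 (Objectives, Aim 2) lists three primary outcomes (goal attainment, caregiver burden and quality of life), and item a speaks of primary outcomes in the plural although it labels only quality of life as primary.

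**Working it through.** **Inputs from the documents.** 22 per arm (section 7, item c; section 4 agrees: "The immediate intervention group (n=22) will receive the intervention during weeks 0-12"); Hedges' g on the between-group difference in change; three primary outcomes in section 2. The plan states no precision figure, so there is none to reproduce.

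**Assumptions.** g is standardised by the pooled SD of change. The thresholds 0.2, 0.3 and 0.5 are illustrations, because the plan gives none.

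1. *Standard error with no true effect.* SE = sqrt(1/22 + 1/22) = 0.302. The small-sample factor with 42 df is J = 1 - 3/(4 × 42 - 1) = 0.982.

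2. *95% interval for g.* With d = g/J, half-width = 1.96 × J × sqrt(2/22 + d²/88).
   - g = 0.3: d = 0.305, half-width 0.58, interval -0.28 to 0.88.
   - g = 0.5: d = 0.509, half-width 0.59, interval -0.09 to 1.09.
   - g = 0.8: d = 0.815, half-width 0.60, interval 0.20 to 1.40.

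3. *Chance of a favourable g when there is no effect.* P(g > c) = P(t with 42 df > c/(0.982 × 0.302)).
   - c = 0.2: 0.25.
   - c = 0.3: 0.158.
   - c = 0.5: 0.049.

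4. *Fewer completers.* If 20% of the 49 recruits are lost, 49 × 0.80 = 39.2. With 20 and 19 completers, SE = 0.320 and P(g > 0.3) = 0.173.

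5. *Different standardiser.* If the baseline SD is used, and variances are equal at the two times, the SD of change is sqrt(2(1 - r)) baseline SDs, where r is the baseline-to-follow-up correlation. By normal approximation, P(g > 0.3) is 0.20 at r = 0.3, 0.16 at r = 0.5 and 0.10 at r = 0.7.

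6. *Three outcomes.* The chance that at least one g exceeds 0.3 with no effect on any is 1 - (1 - 0.158)³ = 0.40 if they are independent. In a simulation of 100,000 trials per setting, it was 0.32 at a between-outcome correlation of 0.5 and 0.28 at 0.7.

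7. *How often the interval would exclude zero.* Approximate two-sided 5% power is Φ(δ/0.302 - 1.96) for a true standardised effect δ: 0.17 at 0.3, 0.38 at 0.5 and 0.76 at 0.8. Unless the true effect is large, the interval will usually include zero, which agrees with the plan's own statement about power.

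**The case against.** The best defence is that this is an openly underpowered pilot whose stated purpose is a first estimate of the effect size. Taking weight off p-values in that setting is good practice, and Hedges' g is a sensible choice. Much of this stands, and it rules out several stronger readings.

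- A reader might infer that the plan has a decision rule under which a large enough g leads to a claim of success and a small one to abandonment. It has none: effect sizes are to be examined, and no success or go/no-go criterion is written.
- A reader might infer that testing has been replaced. The 0.05 level and the GEE models remain, and item a moves emphasis away from significance without removing it.
- A reader might take one trial in six as a property of this plan. It holds only for an assumed threshold of 0.3 and an assumed standardiser.
- A reader might treat the three-outcome figures as a false-positive rate. The plan nowhere says that success on any one outcome counts.
- A reader might infer that an inflated g will be carried into the next trial's sample size. No section says g will be used that way, and g would be inflated only through selection on a favourable result, which the plan does not describe.

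The defence does not reach the central sentence. Obtaining a first estimate is legitimate; examining it for evidence of effectiveness goes further. The GEE models could supply a standard error, but nothing says it will qualify g. The Hedges correction is about 2% (J = 0.982) and leaves sampling error almost unchanged.

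**Conclusion.** The concern holds as a fault of inference and reporting. Followed as written, the text has a point estimate read as evidence of effectiveness on the ground that power is low, which is the very reason the estimate cannot bear that reading alone.

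The firm part of the size is the interval: about 0.59 either side at 22 per arm, so an observed g of 0.3 fits both modest harm and large benefit. The chance figures illustrate the same point and rest on the thresholds and standardiser assumed above: 25%, 16% and 5% for one outcome, and 28% to 40% for at least one of three above 0.3, depending on their correlation. The documents support neither a formal faulty rule nor a claim about the next trial's design.

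This is a cheap improvement. The randomised comparison is unaffected; what changes is what may be concluded from it.

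**What to change.** In section 7, item c, replace the sentence on effect sizes with:

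> Between-group differences in change will be reported in scale points and as Hedges' g, each with a 95% confidence interval, at each time point analysed, with week 12 as the comparison against the untreated waitlist. Comparison with clinically important differences will use the interval, not the point estimate. The results will be described as initial estimates and not as evidence of effectiveness.

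Week 12 is singled out because the waitlist group starts the intervention after it, so week 24 no longer offers an untreated comparison. Bring the benchmark sentence in item a into line, and state there which SD standardises g and which benchmark value applies to each outcome.

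The change is to wording only and needs no further participants, visits or data. Its downside is a less favourable headline, since the interval will usually include zero.
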